6.2.1 Sample size calculations for immunogenicity

The main goals of this trial regarding immunogenicity outcomes involve assessing the ability of FP-conjugate and Trimer 4571 vaccines alone or co-administration to elicit antibody binding FP and envelop trimer antigens and mapping FP-specific serum neutralizing activity induced by the prime vaccines regimens in Groups 5-8 and prime boost vaccines regimens in Groups 7-8. No adjustment for multiple comparisons will be made for the use of multiple assays. The precision with which the true response rate can be estimated from the observed data depends on the true underlying response rate and the sample size. Two-sided 95% CIs for the response rate based on observing a particular rate of responses in the vaccinees is shown in [Table 6-3](#). Calculations are done using the score test method (52). The sample size of n = 13 (Groups 5-6) and n=9 for each of Groups 7 and 8 will be used to evaluate the immunogenicity post the 1st vaccination induced by the vaccination; the sample sizes of n=4, 5 for Groups 7-8 will be used to evaluate the immunogenicity post the 2nd vaccination.

Table 6-3 Two-sided 95% confidence intervals for the true response rate based on observing a particular rate of responses in the vaccinees (n =4, 5, 9, 13)

No. of responses	Observed response rate (%)	95% Confidence interval
2/4	50	[15, 85]
4/4	100	[51, 100]
2/5	40	[11.8, 76.9]
4/5	80	[37.6, 96.4]
3/9	33.3	[12.1, 64.6]
6/9	66.7	[35.4, 87.9]
9/9	100	[70.1, 100]
3/13	23.1	[8.2, 50.3]
6/13	46.2	[23.2, 70.9]
9/13	69.2	[42.4, 87.3]

As shown in [Table 6-4](#), there is limited power for a formal comparison of immunogenicity response rates between Group 7 (n=9) and Group 8 (n=9). For either 80% or 90% power, the sizes of differences that the trial is powered to detect are fairly large. These calculations use a Fisher exact 2-sided test with a type I error rate of 0.05.

Table 6-4 Power for comparison of response rates between 2 arms (n1 = 9, n2 = 9)

True response rate Arm 1 (%)	Minimum true response rate in Arm 2 in order to detect a difference	
	80% power	90% power
10	83	91
20	92	99
30	99	

The response magnitudes will be compared between the arms among the positive responders. The response magnitudes will be transformed (eg, using log-transformation for response magnitudes) prior to the comparisons if they are not normally distributed. The numbers presented in [Table 6-5](#) are the minimum mean differences (in standard deviations [SDs]) between two arms that can be distinguished with a statistical power of 80% or 90% and a type I error rate of 0.05 given a range of possible true response rates in both arms. The calculations are based on 5,000 simulations with the data being generated from normal distributions with different means and a common standard deviation in two arms and the Wilcoxon rank sum test for comparing the difference between arms.

Table 6-5 Minimum mean difference (in SDs) with 80% or 90% power to distinguish the response levels between Group 7 and Group 8 among positive responders.

Common true response rate (%)	Minimum mean difference in SDs (n1 = 9, n2 = 9)	
	Power = 80%	Power = 90%
50	2.7	3.1
60	2.3	2.6
70	2.0	2.3
80	1.8	2.0
90	1.6	1.9
100	1.5	1.8

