3.2 Exploratory objectives

Exploratory objective 1:

Mapping of FP-specific serum neutralizing activity

Exploratory objective 2:

To evaluate the ability of the vaccine regimen to elicit early FP broad neutralizing antibody memory B-cell lineages.

Exploratory objective 3:

To evaluate the humoral and cellular immune response to vaccination regimens including FP-conjugate vaccine and Trimer 4571 to compare responses between the regimens.

Exploratory objective 4:

To conduct analyses related to furthering the understanding of HIV, immunology, vaccines, and clinical trial conduct. To further evaluate immunogenicity of each vaccine regimen, additional immunogenicity assays may be performed in a subset of participants, including on samples from other timepoints, based on the HVTN Laboratory Assay Algorithm.

4 Laboratory strategy

The laboratory strategy for this protocol will focus on interrogations of the humoral and cellular immune response as it relates to the ability of FP-conjugate and Trimer 4571 vaccines to elicit FP-specific binding antibodies. ~~the elicitation of broadly neutralizing antibodies. Magnitude, breadth, kinetics and durability of serum neutralizing antibodies will be assessed by using vaccine-matched and non-matched (heterologous) tier 2 HIV-1 Env pseudotyped viruses in the TZM-bl assay. Serum antibodies will be further interrogated by measuring IgG binding to the vaccine antigens and a specialized set of epitope-domain-specific antigens. A role for T cell help will be investigated by assessing antigen-specific CD4+ T cells by intracellular cytokine staining as measured by flow cytometry. To gain further insights into the requirements for broadly neutralizing antibody induction, exploratory studies may be conducted to assess antigen-specific B-cell frequencies and to interrogate B-cell lineages that give rise to FP-specific antibodies in vaccine recipients. Serum neutralizing antibodies may also be assessed in the TZM-bl assay. The detailed laboratory strategy and the technical details are described in the Central Assay Plan and will be updated as new reagents and techniques are incorporated into assay planning. This document will be available on the protocol webpage. Descriptions of the standard HVTN laboratory assays can be found online at~~
<https://www.hvtn.org/content/dam/hvtn/scientific-programs/hvtn-laboratory-assay-descriptions.pdf>

5 Study design

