5.2.4 Discontinuation of study participation

A participant may be discontinued from protocol participation for the following reasons:

- Participant voluntarily withdraws;
- CRS determines the participant is lost to follow-up;
- The investigational new drug (IND) application Sponsor or regulatory authorities stop the study; or
- PI assessment that it is not in the best interest of the participant to continue participation in the study or that the participant's compliance with the study is not sufficient.

If a participant terminates participation in the study early for any reason, the site principal investigator should consider if the following assessments are appropriate: end-of-study HIV test, complete blood count (CBC) with differential, serum chemistry, physical examination, and if indicated, a pregnancy test (see [Appendix A](#), [Appendix B](#), [Appendix C](#) and [Appendix D](#)). For participants with HIV infection, please see Section [8.7](#). If the site principal investigator has questions regarding a termination visit, they should consult with the PSRT.

6 Statistical considerations

On January 13, 2023, a protocol memo was distributed informing the clinical research sites that all vaccinations in HVTN 303 were permanently discontinued. The sample size calculations for safety and immunogenicity were updated based on the actual numbers of participants who were enrolled in the study and the updated objectives in Section 3. The language shown below is the revised version of the original protocol (v1.0) as per the sample size and the design of the current protocol version 2.0.

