6.5.4 Immunogenicity analysis

6.5.4.1 General approach

For the statistical analysis of immunogenicity endpoints, data from enrolled participants in Part B will be used according to the initial randomization assignment regardless of how many injections the participants received. Additional analyses may be performed, limited to participants who received all scheduled injections per protocol. Assay results from specimens collected outside of the visit window, or from HIV-infected participants collected post infection, may be excluded. Since the exact date of HIV infection is unknown, any assay data from blood draws 4 weeks prior to an infected participant's last seronegative

sample and thereafter may be excluded. If an HIV-infected participant does not have a seronegative sample post enrollment, then all data from that participant may be excluded from the analysis.

Discrete categorical assay endpoints (eg, response rates) will be analyzed by tabulating the frequency of positive response for each assay by antigen and treatment arm at each timepoint for which an assessment is performed. Crude response rates will be presented with their corresponding 95% CI estimates calculated using the score test method (52). Barnard's or Fisher's exact tests, as specified in the SAP, will be used to compare the response rates of any 2 vaccine arms, with a significant difference declared if the 2-sided p-value is ≤ 0.05 . In general, Barnard's is preferred since, under most circumstances, it is more powerful than Fisher's (54).

In addition to response rate estimates for each timepoint, the probability of observing at least 1 positive response by a given timepoint and the probability of observing more than 1 positive response by a given timepoint will be estimated, with corresponding CIs, for each vaccine arm using maximum likelihood-based methods (55).

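### Table 6-4 (protocol 6.2.1): the minimum Arm 2 response rates are 3 to 5 points too high for the two-sided Fisher exact test named, and the blank cell is attainable

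*Protocol*

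**What the plan says.** Protocol section 6.2.1 describes the table as "Table 6-4 Power for comparison of response rates between 2 arms (n1 = 9, n2 = 9") and applies it to Group 7 against Group 8. The method is given in one sentence: "These calculations use a Fisher exact 2-sided test with a type I error rate of 0.05". No approximation, power algorithm or software is named for the table. The column heading presents the entries as the minimum true Arm 2 rate at each power.

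| Arm 1 true rate | 80% power | 90% power |
|---|---|---|
| 10% | 83 | 91 |
| 20% | 92 | 99 |
| 30% | 99 | (blank) |

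The protocol draws a modest conclusion: power for this comparison is limited, and "the sizes of differences that the trial is powered to detect are fairly large". The opening of section 6 presents the figures as current for version 2.0: "The sample size calculations for safety and immunogenicity were updated based on the actual numbers of participants" enrolled.

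For the analysis itself, section 6.5.4.1 leaves the choice between Barnard's and Fisher's test open: "exact tests, as specified in the SAP, will be used to compare the response rates of any 2 vaccine arms". The SAP supplied covers safety only and does not make that choice.

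**The concern.** Every input is fixed by the text: test, sidedness, alpha, 9 per arm and the power targets. With 9 per arm there are only 10 × 10 = 100 possible outcomes, so the power of Fisher's test can be computed exactly. A reader who does this gets a different number in all six cells, and the printed rates are not the minima under the named test.

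The stake is the accuracy of a stated design property. These are the protocol's only power figures for response rates in Group 7 against Group 8. Anyone interpreting a non-significant result would use them to judge what could have been detected, and would conclude that the design was weaker than it is. The blank also suggests that 90% power is out of reach at an Arm 1 rate of 30%, which is not strictly so.

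**Working it through.** **Inputs (protocol 6.2.1):** n1 = n2 = 9; Fisher exact, two-sided, reject if p ≤ 0.05; Arm 1 rates 10%, 20%, 30%; power 80% and 90%. All 9 per arm are taken as evaluable, as the table does.

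**Step 1. Reproduce the printed cells.** The continuity-corrected arcsine (Walters) approximation to the power of Fisher's test is

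power ≈ Φ( √18 × [asin√(p2 − 1/18) − asin√(p1 + 1/18)] − 1.96 ),

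where 1/18 = 1/(2 × 9). For p1 = 0.10 and p2 = 0.83, the bracket is 1.0759 − 0.4054 = 0.6705. Then √18 × 0.6705 − 1.96 = 0.885, and Φ(0.885) = 81.2%. At p2 = 0.82 the result is 79.8%, so the smallest whole percent is 83, as printed. The other cells follow in the same way:

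| Arm 1 | Target | Smallest Arm 2 rate (approximation) | Power there | One point lower |
|---|---|---|---|---|
| 10% | 80% | 83 | 81.2% | 79.8% |
| 10% | 90% | 91 | 90.7% | 89.7% |
| 20% | 80% | 92 | 80.4% | 78.7% |
| 20% | 90% | 99 | 91.3% | 89.9% |
| 30% | 80% | 99 | 81.5% | 79.2% |
| 30% | 90% | none (maximum 83.8%) | – | – |

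All six cells match, including the blank. Other candidates do not match the full table: the doubled one-sided Fisher p-value, smaller alphas, other sample sizes, the normal formula with and without continuity correction, and the uncorrected arcsine. Dropping the borderline outcomes 1/9 v 6/9 and 3/9 v 8/9 (p = 0.0498) gives 83/90, 93/97 and 98/100, which also fails.

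**Step 2. Exact rejection region.**

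| Arm 1 responders | Smallest rejecting Arm 2 count | p at that count |
|---|---|---|
| 0 | 5 | 0.029 |
| 1 | 6 | 0.0498 |
| 2 | 8 | 0.015 |
| 3 | 8 | 0.0498 |
| 4 | 9 | 0.029 |

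With 5 or more Arm 1 responders, no higher Arm 2 count rejects; 5/9 v 9/9 has p = 0.082.

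**Step 3. Exact power.** Power is the sum over Arm 1 counts a of P(X1 = a) × P(X2 ≥ threshold for a). Rejections in the opposite direction are negligible here. For 10% against 78%:

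- a = 0: 0.3874 × 0.9709 = 0.3761
- a = 1: 0.3874 × 0.8856 = 0.3431
- a = 2: 0.1722 × 0.3782 = 0.0651
- a = 3: 0.0446 × 0.3782 = 0.0169
- a = 4: 0.0074 × 0.1069 = 0.0008

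The sum is 0.802. At 77% it is 78.8%, so 78 is the smallest whole percent that reaches 80%.

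**Step 4. All cells on a 1-point grid.**

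| Arm 1 | Target | Printed | Exact power at printed | Exact minimum | Power there (one point lower) | Printed − exact | Approximation at exact minimum |
|---|---|---|---|---|---|---|---|
| 10% | 80% | 83 | 86.8% | 78 | 80.2% (78.8%) | 5 | 73.9% |
| 10% | 90% | 91 | 95.1% | 86 | 90.2% (89.1%) | 5 | 85.1% |
| 20% | 80% | 92 | 86.9% | 89 | 81.0% (78.9%) | 3 | 75.1% |
| 20% | 90% | 99 | 97.3% | 94 | 90.5% (88.7%) | 5 | 83.8% |
| 30% | 80% | 99 | 88.5% | 96 | 82.3% (79.97%) | 3 | 74.6% |
| 30% | 90% | blank | – | 100 | 90.1% (88.5%) | – | 83.8% |

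Simulation with 400,000 draws per cell agrees at all five printed rates (86.8%, 95.1%, 86.9%, 97.3%, 88.5%). On a 0.1-point grid the minima are 77.9/85.8, 88.6/93.8 and 95.1/100.

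**Step 5. The blank cell by hand.** At a true Arm 2 rate of 100%, Arm 2 is always 9/9. Fisher's test then rejects when Arm 1 has 4 or fewer responders, so power = P(Binomial(9, 0.3) ≤ 4) = 0.0404 + 0.1556 + 0.2668 + 0.2668 + 0.1715 = 90.1%. At an Arm 1 rate of 40% the same sum is 73.3%, so leaving out a 40% row is correct.

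**The case against.** The strongest reply is that the table is not miscalculated. Its cells follow from the protocol's own test, sample size, alpha and sidedness under a recognised approximation to the power of Fisher's test, and the text never says that power was enumerated. The match is complete, and the inputs and the named test are not in question. It does not rescue the figures: the text discloses no approximation, exact calculation is trivial at this size, and the approximation understates power by 5 to 8 points at the exact minima. That the authors used it is inferred from the match, and the discrepancy does not depend on that inference.

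A second reply is that little follows from the error. Enrolment had ended and vaccination had stopped before version 2.0 was written, so the table could not influence sample size. The smallest exact detectable difference is still 96 − 30 = 66 points. This stands, and it limits the weight of the finding.

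A third is that the 30% row is delicate. Exact power at 95% is 79.97%, so 96 depends on the whole-percent grid, and 100% is a boundary value that an author might reasonably leave blank. This is fair, and a footnote deals with it. It does not affect the printed 99, where exact power is 88.5%.

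Finally, placing the comparison under exploratory objective 3 ("to compare responses between the regimens") is a reading of the protocol. Section 6.2.1 does not make the link, and response rate also appears in primary endpoint 2.

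**Conclusion.** The concern holds. Under the stated test, five printed cells exceed the true minima by 3 to 5 points, and the sixth is blank although 90% power is just attainable at a true Arm 2 rate of 100%. Exact power at the five printed rates is 86.8%, 95.1%, 86.9%, 97.3% and 88.5%. This rests on 9 evaluable participants per arm, independent binomial responses, rejection at a two-sided Fisher p ≤ 0.05, and minima rounded up to whole percents.

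The error is conservative: the design can detect somewhat smaller differences than printed. No sample size or decision rule rests on the table, and the protocol's conclusions about limited power and large detectable differences stand. It is a correction of stated figures only.

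**What to change.** Replace the Table 6-4 entries with the exact values:

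| Arm 1 true rate | 80% power | 90% power |
|---|---|---|
| 10% | 78 | 86 |
| 20% | 89 | 94 |
| 30% | 96 | 100* |

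*Reached only at a true Arm 2 rate of 100%.

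Add that power was obtained by enumeration. The test remains Fisher's; if Barnard's test is chosen under section 6.5.4.1, recompute the table for that test. Naming the approximation beside the present figures would be the bare minimum, but the exact values cost no more and make the table agree with its own description.

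The cost is six cells in one protocol table. Conduct, data, test and sample size are untouched.

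Optionally, one sentence could be added to Table 6-5, which is also in section 6.2.1. It says "The calculations are based on 5,000 simulations with the data being generated from normal distributions" but not how responder counts, runs with too few responders to test, or the Wilcoxon p-value were handled. The 50% and 60% rows depend on this. No error in Table 6-5 is claimed.

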Some immunologic assays have underlying continuous or count-type readout that are dichotomized into responder/nonresponder categories (eg, nAb, BAMA, ICS). If treatment arm differences for these assays are best summarized by a mixture model, then either Lachenbruch's test statistic (57) or an alternative 2-part test (58) (as defined in the SAP) will be used to evaluate the composite null hypothesis of equal response rates in the 2 arms and equal response distributions. Lachenbruch's test statistic equals the square of a binomial Z-statistic for comparing the response rates plus the square of a Wilcoxon statistic for comparing the response distributions in the subgroup of responders. A permutation procedure is used to obtain a 2-sided p-value. For estimation, differences in response rates between arms will be estimated using the methods described above, and in the subgroup of positive responders, differences in location parameters between arms will be estimated using the methods described above.

More sophisticated analyses employing repeated measures methodology (for example, linear mixed models or marginal mean models fit by generalized estimating equations [GEE]) may be utilized to incorporate immune responses over several timepoints and to test for differences over time. However, inference from such analyses would be limited by the small sample size of this study. All statistical tests will be 2-sided and will be considered statistically significant if $p \leq 0.05$.

Based upon previous HVTN trials, missing 15% of immunogenicity results for a specific assay is common due to study participants terminating from the study early, problems in shipping specimens, or low cell viability of processed PBMCS. To achieve unbiased statistical estimation and inferences with standard methods applied in a complete-case manner (only including participants with observed data in the analysis), missing data need to be missing completely at random (MCAR). Following the most commonly used definition, MCAR assumes that the probability of an observation being missing does not depend on any participant characteristics (observed or unobserved). When missing data are minimal (specifically if no more than 20% of participants are missing any values), then standard complete-case methods will be used, because violations of the MCAR assumption will have little impact on the estimates and hypothesis tests.

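### Table 6-5 credits 9 participants per arm with more power at a true 50% response rate than a Wilcoxon test among responders can deliver; the 60% row depends on which version of the test is used

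*Protocol*

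**What the plan says.** Protocol Section 6.2.1 sets out the magnitude comparison: "The response magnitudes will be compared between the arms among the positive responders". Table 6-5 gives minimum mean differences in SD units "with a statistical power of 80% or 90% and a type I error rate of 0.05 given a range of possible true response rates", for n1 = n2 = 9 (Group 7 and Group 8). Its rows are indexed by "Common true response rate", from 50% to 100%. The figures come from 5,000 simulations of normal data with a common SD, analysed with "the Wilcoxon rank sum test for comparing the difference between arms". Section 6.5.4.1 fixes the sidedness: "All statistical tests will be 2-sided and will be considered statistically significant if" p is at most 0.05.

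The two rows at issue:

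| True response rate | 80% power | 90% power |
|---|---|---|
| 50% | 2.7 SD | 3.1 SD |
| 60% | 2.3 SD | 2.6 SD |

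The text does not say whether the Wilcoxon test is exact or approximate. It does not say how the number of responders was set in each replicate, or what was done with replicates that had too few responders to test.

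**The concern.** A true response rate applied to 9 participants implies a random number of responders. At 50%, many trials would have only 2 or 3 responders in an arm. With so few observations a rank test may be unable to reach p ≤ 0.05 even when the two arms do not overlap at all. Power then has a ceiling that no effect size can lift, yet the 50% row prints finite differences for both targets.

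Magnitude is part of primary endpoint 2 (Section 3.1), and Table 6-5 is the only power statement for it. The introduction to Section 6 says these calculations were updated for version 2.0, and the SAP covers safety only (SAP Section 2), so nothing elsewhere replaces the table. A reader who relies on the 50% row would credit a non-significant Group 7 versus Group 8 comparison with more sensitivity than the design has.

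**Working it through.** **Inputs.** n1 = n2 = 9, comparison among responders, Wilcoxon rank sum test, normal data with SD 1, type I error 0.05 (all Section 6.2.1); two-sided (Section 6.5.4.1). Assumption: responders in each arm follow Binomial(9, p) independently, and a trial that cannot be tested counts as a non-rejection.

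**Step 1: which responder counts can reject.** With a and b responders, the smallest two-sided exact p-value is 2/C(a+b, a):

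- 3 v 3: 2/20 = 0.100
- 3 v 4: 2/35 = 0.057
- 4 v 4: 2/70 = 0.029
- 3 v 5: 2/56 = 0.036
- 2 v 7: 2/36 = 0.056
- 2 v 8: 2/45 = 0.044

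Rejection is possible only with at least 4 in each arm, 3 against at least 5, or 2 against at least 8.

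**Step 2: ceiling at p = 50%, exact test.** The Binomial(9, 0.5) weights, out of 512, for 0 to 9 responders are 1, 9, 36, 84, 126, 126, 84, 36, 9, 1.

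- Both arms at least 4: (382/512)² = 0.5567
- 3 against at least 5: 2 × (84/512) × (256/512) = 0.1641
- 2 against at least 8: 2 × (36/512) × (10/512) = 0.0027
- Total: 0.7235

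The other 27.7% of trials cannot reject at any difference.

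**Step 3: ceiling under the approximations.** With continuity correction, 2 v 8 can no longer reject and the ceiling is 72.1%. Without correction, 3 v 3, 3 v 4, 2 v 6 and 2 v 7 can also reject. They add (84/512)² + 2(84 × 126)/512² + 2(36 × 84)/512² + 2(36 × 36)/512² = 0.0269 + 0.0807 + 0.0231 + 0.0099 = 0.1406, so the ceiling is 0.8641. Part of that gain comes from rejecting at 3 v 3, where the exact p-value is 0.10.

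**Step 4: power at the printed differences.** Simulated power for each pair of counts (a, b), weighted by the binomial probabilities. Each cell shows power at the printed 80% and 90% differences.

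| Row | Printed SDs | Exact | Uncorrected approximation |
|---|---|---|---|
| 50% | 2.7 / 3.1 | 64% / 68% | 76% / 81% |
| 60% | 2.3 / 2.6 | 77% / 84% | 83% / 89% |
| 70% | 2.0 / 2.3 | 81% / 89% | 84% / 91% |
| 80% | 1.8 / 2.0 | 82% / 89% | 84% / 90% |
| 90% | 1.6 / 1.9 | 81% / 92% | 82% / 92% |
| 100% | 1.5 / 1.8 | 80% / 92% | 83% / 94% |

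Rows 70% to 100% reproduce the table under the exact test to about 2 points. With continuity correction the 50% row is about 63% / 67% and the 60% row about 76% / 83%.

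Simulation noise does not explain the gap. With 5,000 replicates the standard error near 80% is √(0.8 × 0.2/5000) = 0.6 points. A direct 5,000-replicate run of the exact test at 50% gave 62.9% at 2.7 SD, 68.2% at 3.1 SD and 71.8% at 50 SD.

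**Step 5: differences that would be needed.**

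- 50% row: neither target is attainable with the exact or continuity-corrected test. Without correction, 80% needs about 3.0 SD and 90% is unattainable.
- 60% row, exact test (ceiling 92.3%): about 2.4 to 2.5 SD for 80% and 3.2 to 3.3 SD for 90%.

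**Step 6: fixed responder counts.** At 2.7 / 3.1 SD the exact test gives 75% / 85% with 4 v 4, 85% / 93% with 4 v 5, and 91% / 96% with 5 v 5. At 2.3 / 2.6 SD, 5 v 5 gives 80% / 88%.

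**The case against.** **The table may condition on responder counts.** Section 6.2.1 names normal data as what was generated and mentions no draw of responder numbers. If counts were fixed at the whole number below 9p, the exact test gives about 80% / 88% in the 60% row (5 v 5), 83% / 91% at 70%, 81% / 89% at 80%, 82% / 92% at 90% and 80% / 92% at 100%. All fit. The 50% values lie between the 4 v 4 and 5 v 5 results, where 9p = 4.5. This is a credible account of how the table was built, and it means a reader should not infer that 90% power is impossible however the calculation is set up. But it is power given a responder count, and the table is labelled by a true response rate with 9 per arm. At a true 50% rate, both arms have 4 or more responders only 55.7% of the time.

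**The test is never called exact.** That is so. The inference that neither target can be reached in the 50% row holds for the exact and continuity-corrected tests, but the documents do not establish it for every Wilcoxon version. Without correction 80% is reachable, though not at 2.7 SD.

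**Section 6.5.4.1 allows a t-test when data look normal.** With binomial responders a t-test at the printed values gives about 86% / 92% (50% row) and 88% / 93% (60% row). The analysis itself may therefore do better than the Wilcoxon figures here. That does not rescue a table stated to be Wilcoxon power.

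**The stakes are modest.** Primary objective 2 specifies no Group 7 versus Group 8 test; comparing regimens is exploratory objective 3. Enrolment had closed, so no sample size turns on the table. Section 6.2.1 already calls power for the response-rate comparison limited, although that remark concerns Table 6-4. A reader might infer that the plan treats a null result as excluding the printed differences. No section says so, and power of 64% to 84% is not an inability to detect.

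**Conclusion.** The 50% row is wrong as labelled. With 9 per arm and responder counts that vary with a true 50% rate, power at 2.7 SD is about 64% (exact) to 76% (uncorrected approximation) against 80% stated. At 3.1 SD it is about 68% to 81% against 90% stated. On that reading 90% cannot be reached at any difference: the ceiling is 72% or 86%, depending on the version of the test.

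The 60% row is conditional. It is too favourable under the exact or continuity-corrected test (about 77% / 84% exact, 76% / 83% corrected) but acceptable under the uncorrected approximation (83% / 89%) or with 5 fixed responders per arm. In that row it is the power that would be overstated; the printed differences would be too small. Rows 70% to 100% stand.

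This rests on independent binomial responder counts, normal magnitudes with a common SD, a two-sided 0.05 test, and untestable trials counted as non-rejections. It is worth correcting because it misstates a power figure for a primary endpoint component, but it changes no enrolment or design decision.

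**What to change.** Re-run Table 6-5 drawing the responders in each arm from Binomial(9, p), count replicates with too few responders as non-rejections, and state which Wilcoxon version is used.

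- **50% row, exact test:** print not attainable in both columns, with maximum power 72%.
- **50% row, uncorrected approximation:** print about 3.0 SD for 80%, and not attainable, with maximum power 86%, for 90%.
- **60% row:** update to match the chosen test (about 2.4 to 2.5 and 3.2 to 3.3 SD if exact; the present values can broadly stand if uncorrected).

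If the sponsor prefers power at fixed responder counts, the rows should be relabelled by the number of responders per arm rather than by a true response rate.

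The cost is one short simulation, one corrected table and a sentence on method. The 50% row, and possibly the 60% row, will look less favourable.
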